10. STATISTICAL CONSIDERATIONS

10.1 Study Endpoints, Analysis Sets, and Covariates

10.1.1 Study Endpoints

10.1.1.1 Phase 1

10.1.1.1.1 Monotherapy (Parts 1a, 1b, and 2a)

10.1.1.1.1.1 Primary Endpoints:

- Safety: subject incidence of treatment-emergent adverse events, treatment-related adverse events, and clinically significant changes in vital signs, physical examinations, ECGs, and clinical laboratory tests
- Subject incidence of DLT

10.1.1.1.1.2 Secondary Endpoints:

- PK parameters of AMG 510 including, but not limited to C_{max} , time to achieve C_{max} (t_{max}), and AUC
- ORR, DOR, DCR, **PFS**, duration of stable disease, **and TTR** measured by CT or MRI and assessed per **RECIST** 1.1. Response will be assessed by independent radiologic review. Complete response and PR require confirmatory CT or MRI repeat assessment 4 weeks after the first detection of response.
- PK parameters of AMG 510 including, but not limited to, C_{max} , t_{max} , and AUC in the fed and fasted state
- AMG 510 exposure/QTc interval relationship

10.1.1.1.1.3 Exploratory Endpoints:

- AMG 510 exposure/safety and exposure/efficacy relationships
- AMG 510 excretion in urine
- Characterization of potential metabolites of AMG 510 in plasma and urine, if appropriate
- **Pharmacodynamic changes observed in blood and/or biopsies if available**
- Quantification of biomarker expression at protein, RNA, and DNA levels, as appropriate
- Potential biomarkers by biochemical and/or genetic analysis of blood and/or tumor tissue samples

[REDACTED]

Approved

[REDACTED]

[REDACTED]

10.1.1.2 Phase 2 (Monotherapy)

10.1.1.2.1 Primary Endpoint

- Objective response rate (ORR = CR + PR), measured by CT or MRI and assessed per **RECIST** 1.1. Response will be assessed by independent radiologic review. Complete response and PR require confirmatory CT or MRI repeat assessment 4 weeks after the first detection of response.

10.1.1.2.2 Secondary Endpoints

- DOR - defined as time from first evidence of confirmed PR or CR to disease progression or death due to any cause, whichever occurs first. Subjects without a duration ending event will be censored at their last evaluable disease assessment date. Progression will be based on an independent radiologic assessment of disease response per **RECIST** 1.1.
- DCR defined as CR + PR + stable disease rate measured as described for ORR.
- PFS - defined as time from first dose of AMG 510 until disease progression or death from any cause, whichever occurs first. Subjects who do not progress or die will be censored at their last evaluable disease assessment date. Progression will be on an independent radiologic assessment of disease response per **RECIST** 1.1.
- OS - defined as time from first dose of AMG 510 until death from any cause. Subjects who do not die will be censored at the date of last contact.
- PFS rate at 6 months and 12 months.
- OS rate at 12 months.
- Incidence and severity of adverse events.
- PK parameters of AMG 510 including, but not limited to, C_{max} , t_{max} , and AUC.
- **TTR - defined as time from first dose of AMG 510 until the first evidence of confirmed PR or CR.**

Approved

10.1.1.2.3 Exploratory Endpoints

- AMG 510 exposure/safety and exposure/efficacy relationships
- **Pharmacodynamic changes observed in blood and/or biopsies if available**
- Biomarkers of response and resistance to AMG 510 at the time of progression
 - Quantification of biomarker expression at protein, RNA, and DNA levels, as appropriate
 - Potential biomarkers by biochemical and/or genetic analysis of blood and/or tumor tissue samples
- Changes in cancer-specific symptoms and overall health status using subject-reported outcome instruments:
 - Impact of treatment on disease-related symptoms and HRQOL (instruments; EORTC QLQ-C30 + disease-specific modules QLQ LC13 **and NSCLC SAQ** for NSCLC, and QLQ Pan 26 for pancreatic cancer)
 - Treatment-related symptoms and impact on the subject (**EORTC QLQ-C30**, selected questions from the PRO-CTCAE library and a single item about symptom bother, **item GP5 of the FACT-G**)
 - Physical function (instrument: EORTC QLQ-C30, **Physical function scale**)

10.1.2 Analysis Sets

10.1.2.1 Safety Analysis Set

The safety analysis set (SAS) will consist of all subjects who receive at least one dose of AMG 510. The analysis of all safety endpoints, unless noted otherwise, will be conducted on the SAS. For the phase 1 part of the study, the analysis of DLT will be restricted to DLT-evaluable subjects (see [Section 3.3](#) for definition).

10.1.2.2 Pharmacokinetic Analysis Set

The PK Analysis Set will contain all subjects who have received at least 1 dose of the investigational product and have at least 1 PK sample collected. These subjects will be evaluated for PK analysis unless the number of data points required for analysis is not enough, or significant protocol deviations have affected the data, or if key dosing or sampling information is missing.

10.1.2.3 Phase 1 Monotherapy RP2D ORR Analysis Set

The phase 1 monotherapy RP2D ORR analysis set (P1OAS) will consist of all subjects with confirmed *KRAS*^{p.G12C} status whose initial dose of AMG 510 is at the RP2D and received at least 1 dose of AMG 510 in the phase 1 monotherapy dose exploration part, or the phase 1 monotherapy dose expansion part, and had at least 6-week response data. Subjects who stopped disease assessments prior to 6 weeks will be included in this analysis set if the data cutoff is at least 6 weeks after their first dose date. The futility and efficacy thresholds will be calculated for

monitoring the antitumor activity of monotherapy of AMG 510 during phase 1 expansion part using this analysis dataset.

10.1.2.4 Phase 2 Full Analysis Set

The phase 2 full analysis set (P2FAS) will consist of all phase 2 subjects who received at least 1 dose of AMG 510. The primary analysis (excluding the analysis of ORR) and the final analysis will be performed on the P2FAS.

10.1.2.5 Phase 2 ORR Analysis Set

The phase 2 ORR analysis set (P2OAS) will consist of all subjects in the phase 2 full analysis set who have had at least 6 weeks response data starting from day 1. Subjects who stopped disease assessments prior to 6 weeks will be included in this analysis set if the data cutoff is at least 6 weeks after their first dose date. The interim futility analysis and primary analysis of ORR will be performed on the P2OAS.

10.1.3 Covariates and Subgroups

10.1.3.1 Covariates

The relationship between covariates and efficacy endpoints may be explored if appropriate.

10.1.3.2 Subgroups

Subgroup analysis will be performed by tumor type. Other potential subgroups will be pre-specified in the statistical analysis plan.

10.2 Sample Size Considerations

10.2.1 Phase 1

Phase 1 part 1 – Dose Exploration: No more than 92 subjects will be enrolled in the dose exploration part of the study. Approximately 30 subjects enrolled in cohorts of $n = 2-4$ subjects ($n = 4-8$ at the highest planned dose level) will be used to estimate the monotherapy QD dosing MTD. [REDACTED]

[REDACTED]

[REDACTED] These sample sizes are based on practical considerations and are consistent with conventional oncology studies with the objective to estimate the MTD and to evaluate initial safety and tolerability. The probability of observing at least

Approved

1 DLT if the true DLT rate is 10 to 33% is provided in [Table 8](#) for various number of subjects.

Table 8. Probability of Observing at Least 1 DLT

Number of Subjects	10% DLT Rate	33% DLT Rate
2	19	55
3	27	70
4	34	80
6	47	91
8	57	96
10	65	98
12	72	99

DLT = dose limiting toxicity

In order to better estimate the RP2D and to better characterize the safety, efficacy, PK, and pharmacodynamics for AMG 510 monotherapy, an additional 20 to 40 subjects may be enrolled to one or more monotherapy dose levels that have been shown to be safe and tolerable from which at least 6 subjects will be evaluated for food effect. The sample size of at least 6 subjects for food effect **assessment** is based on practical considerations and judged sufficient for the evaluation; no formal calculation was made.

Phase 1 part 2– Dose Expansion: **The maximum sample size in the dose expansion part to evaluate AMG 510 monotherapy is 60 in subjects with *KRAS p. G12C* mutant advanced solid tumor types. The actual sample size will depend on DLRT review with monitoring criteria defined in [Section 10.4.1.2](#).** With 20 subjects receiving monotherapy AMG 510 in dose expansion, there is an 88% to 99% probability of observing at least 1 adverse event if the true event rate is 10% to 20% with 60 subjects there is a 45% to 95% probability of observing at least 1 adverse event if the true event rate is 1% to 5%.

The ORR will be reported by tumor types. For NSCLC, with 60 subjects, 95% of the times the true ORR will be between 0.188 and 0.432, when the observed ORR is 0.3; and when the true ORR is 0.3, the chance that the 95% CIs of ORR will be > 0.15 is 76%. For CRC, with 60 subjects, 95% of the times the true ORR will be between 0.108 and 0.323, when the observed ORR is 0.2; and when the true ORR is 0.2, the chance that the 95% CIs of ORR will be > 0.05 is 93%. Below table describes the scenarios with sample size of 20 to 60.

Table 9. Sample Size Justification

NSCLC		
Sample Size	95% Exact CI of the True ORR Given an Observed ORR = 0.3	Probability (ORR 95% CI Lower Bound > 0.15) Given True ORR = 0.3)
20	(0.119, 0.543)	39%
30	(0.147, 0.494)	41%
40	(0.166, 0.465)	56%
50	(0.179, 0.446)	67%
60	(0.188, 0.432)	76%
CRC		
Sample Size	95% Exact CI of the True ORR Given an Observed ORR = 0.2	Probability (ORR 95% CI Lower Bound > 0.05) given true ORR = 0.2)
20	(0.057, 0.437)	59%
30	(0.077, 0.386)	75%
40	(0.091, 0.356)	84%
50	(0.100, 0.337)	90%
60	(0.108, 0.323)	93%

ORR = objective response rate

[REDACTED]

Approved

10.2.2 Phase 2

The phase 2 part of the study will target an ORR over a benchmark rate to exclude based on the lower limit of the 95% CI for the observed ORR for each tumor type (NSCLC, CRC).

For NSCLC subjects, a large phase 3 trial (REVEL) for second-line treatment after disease progression on platinum-based therapy showed that an ORR of 23% was observed with ramucirumab plus docetaxel (Garon et al 2014, NCT01168973).

For CRC subjects, although the treatment for ≥ third line subjects with Regorafenib or TAS 102 has demonstrated ORR of only 1% to 4% (Li et al, 2015; Mayer et al, 2015; Grothey et al, 2013), these therapies has demonstrated survival

benefits. To justify the use of surrogate endpoint ORR in this phase 2 trial, a higher benchmark ORR for CRC is selected.

The benchmark ORR to exclude is selected as 23% for NSCLC and 10% for CRC. No benchmark ORR will be set for tumor types other than NSCLC and CRC because of low expected enrollment. A sample size of 105 subjects for NSCLC and 60 subjects for CRC will provide approximately a 90% probability that the lower limit of the ORR 95% CI exceeds the tumor-specific benchmark ORR.

The minimum observed ORRs that would exclude the benchmark ORR with 105 NSCLC subjects and 60 CRC subjects are 32% and 20%, respectively.

10.3 Adaptive Design

For phase 1 dose exploration, the adaptive features of the BLRM design are described in [Appendix E](#). For phase 1 dose expansion, the futility and efficacy thresholds are calculated and specified in [Section 10.4.1.2](#). For phase 2, futility analyses are described in [Section 10.4.1.3.2](#).

10.4 Planned Analyses

10.4.1 Interim Analyses

10.4.1.1 Phase 1 (Part 1 - Dose Exploration)

Safety data will be reviewed on an ongoing basis by Amgen. Based on accumulating toxicity information, BLRM will be used to make dosing recommendations. After each cohort completes enrolment and after all DLT-evaluable subjects within the cohort have completed the DLT window, Amgen, in consultation with DLRT, will review the DLRM recommended dose level and will review all available cumulative data by cohort prior to making dose exploration decisions. As a sensitivity analysis, a one-parameter Continual Reassessment Method (CRM) model may be used to estimate the dose-toxicity relationship to help making dose escalation decisions. Adverse events and DLTs observed in all subjects will be evaluated continually and considered in all enrollment and dosing decisions.

The DLRT will be composed of the investigators, Amgen Medical Monitor, Amgen Global Safety Officer, Amgen Early Clinical Development Manager, and Biostatistics representative. Additional members may be added as needed (eg, PK Scientist). A quorum, defined as the majority of actively screening and enrolling investigators or their qualified designee (ie, sub-investigator possessing hard copy documentation [eg, email] of the investigator's recommendation regarding the dose level review), must be in

attendance for DLRM to proceed. The DLRM will be rescheduled if a quorum is not reached. Voting members of the DLRM will include the Amgen medical monitor, the Amgen global safety officer, and all actively screening and enrolling investigators or their qualified sub-investigator designee. The team may recommend escalation to the next planned dose, escalation to an intermediate dose (a dose lower than the next planned dose), continuation or delay in dosing, repetition or expansion of a cohort, de-escalation to a lower dose, or termination of the study. The Amgen medical monitor and Global Safety Officer and the majority of actively screening and enrolling investigators participating in the DLRM must cast a positive vote indicating an acceptable safety profile was observed for AMG 510 to allow the dose level modification and/or cohort continuation/expansion to proceed. All available study data including demographics, smoking status (prior and current), medical history, concomitant medications, AEs, ECGs, vital signs, laboratory results, emerging PK or pharmacodynamics, and emerging efficacy data will be reviewed.

The following recommendations will be made by the DLRT:

- dose escalation/de-escalation decisions
- number of subjects per cohort
- continuation, delay or termination of dosing
- change of the dosing schedule
- termination of the study

10.4.1.2 Phase 1 (Part 2 - Dose Expansion)

This same DLRT will be responsible for reviewing data in the dose expansion phase to confirm the RP2D and determine the benefit/risk of proceeding to the phase 2 part of the study. The dose expansion part of the study (phase 1 - part 2) can open once an MTD or a RP2D and dosing schedule has been estimated in the dose exploration part of the study (phase 1 – part 1). If no DLT is observed in phase 1 – part 1, the RP2D will be estimated based on composite review of PK, overall safety/tolerability, and observed responses. Further confirmation of the RP2D dose will be sought in the phase 1 part 2 dose expansion.

In the dose expansion, additional subjects will be enrolled at the RP2D estimated in the phase 1 part 1 dose exploration. After a minimum of 20 subjects have been enrolled to the initial estimated monotherapy RP2D (including subjects enrolled to the RP2D in either the dose exploration [approximately 6] or the dose expansion [approximately 14] parts of the study) and have completed the 21-day DLT period, and after a minimum of

10 of these subjects have at least 6 weeks of response data (including all previous data from the dose expansion and backfill cohorts), the DLRT will review all available safety, laboratory, PK, and efficacy (physician assessment) data.

After **the** first review has been conducted, if a decision is made to continue to obtain additional data at the initial estimated RP2D prior to proceeding to phase 2, the intervals for subsequent reviews will be determined by the DLRT but should occur within a maximum of 20 additional subjects enrolled and dosed for 21 days. The maximum number of subjects that may be enrolled to the initial estimated RP2D in the monotherapy dose expansion group, without confirmation of this dose for phase 2, will not exceed 60. If another dose (or schedule) needs to be explored, additional subjects on that dose (or schedule), up to a total of 60, may be enrolled.

Based on emerging clinical efficacy data, the number of subjects with specific tumor types may be restricted/specified in the expansion part.

Antitumor activity will be monitored in terms of ORR by tumor types (NSCLC, CRC). Futility and efficacy thresholds will be calculated using Bayesian posterior probability approach based on the cumulative efficacy data and it will serve as a guidance to the DLRT. Enrollment will not be held to conduct this assessment.

Whenever DLRT will review the data, and there are at least 5 evaluable subjects in the tumor type, the futility and efficacy thresholds for that tumor type will be calculated using all the cumulative efficacy data in phase 1 Monotherapy RP2D ORR Analysis Set to provide the guidance. In the calculation of thresholds, a response is defined as either a confirmed or unconfirmed CR or PR as per RECIST 1.1.

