10.4.1.2.1 Futility Thresholds

For NSCLC, the futility thresholds are calculated such that the Bayesian posterior probability of a true ORR ≤ 0.15 is $>$ a high probability of 75%. For CRC, the futility thresholds are calculated such that the Bayesian posterior probability of a true ORR ≤ 0.05 is $>$ than a high probability of 75%. A noninformative prior distribution of beta (1, 1) will be used.

NSCLC: probability (ORR ≤ 0.15) $>$ 75%

CRC: probability (ORR ≤ 0.05) $>$ 75%

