10.4.1.2.2 Efficacy Thresholds

For NSCLC, the efficacy thresholds are calculated such that the Bayesian posterior probability of a true ORR > 0.25 is \geq to a high probability of 60%. For CRC, the efficacy thresholds are calculated such that the Bayesian posterior probability of a true ORR > 0.1 is \geq to a high probability of 60%. A noninformative prior distribution of beta (1, 1) will be used.

NSCLC: probability [ORR > 0.25] $\geq 60\%$

CRC: probability [ORR > 0.1] $\geq 60\%$

Table 10 and **Table 11** are look up tables calculated for NSCLC and CRC, providing the detailed futility and efficacy thresholds with different numbers of response-evaluable subjects (having at least 6-week response data) when DLRT review the data. For example, at the time when DLRT plan to review the data, there are a total of 25 response-evaluable NSCLC subjects. If observing number of the response is ≤ 2 , based on the table, the guidance will recommend not to continue due to the lack of efficacy. If observing number of the response is ≥ 7 , the guidance will recommend continuing to phase 2. If the observing number of the response is in between and the total number of response-evaluable subjects at that RP2D has not reached the maximum 60, the guidance will recommend enrolling more patients in the phase 1 expansion cohort.

The operating characteristics of these thresholds are demonstrated assuming a minimal of 5 response-evaluable subjects per tumor type for the first DLRT review and every 5 response-evaluable subjects thereafter. The actual sample size per tumor type at each look will depend on tumor type distribution. **Table 12** and **Table 13** show the cumulative probabilities of recommending DLRT to stop the trial due to lack of efficacy and the cumulative probabilities of recommending DLRT to continue to phase 2 given the true ORR ranging from 0.1 to 0.5 for NSCLC subjects and 0.05 to 0.25 for CRC subjects.

Approved

Table 10. Look Up Table for NSCLC Subjects

Number of Subjects	Recommend Not to Continue if Observing the Number of Responses Below
5 ~ 7	Never stop for futility with this number of subjects
8 ~ 16	0
17 ~ 24	≤ 1
25 ~ 31	≤ 2
32 ~ 39	≤ 3
40 ~ 47	≤ 4
48 ~ 54	≤ 5
55 ~ 60	≤ 6
Number of Subjects	Recommend Go to Phase 2 if Observing the Number of Responses below
5 ~ 8	≥ 2
9 ~ 11	≥ 3
12 ~ 15	≥ 4
16 ~ 19	≥ 5
20 ~ 23	≥ 6
24 ~ 26	≥ 7
27 ~ 30	≥ 8
31 ~ 34	≥ 9
35 ~ 38	≥ 10
39 ~ 42	≥ 11
43 ~ 46	≥ 12
47 ~ 50	≥ 13
51 ~ 54	≥ 14
55 ~ 57	≥ 15
58 ~ 60	≥ 16

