- **New lesions** – The term “new lesion” always refers to the presence of a new finding that is definitely tumor. New findings that only may be tumor, but may be benign (infection, inflammation, etc.) are not selected as new lesions, until that time when the review is certain they represent tumor.
 - If a new lesion is equivocal, for example because of its small size, continued therapy and follow-up evaluation will clarify if it represents truly new disease. If repeat scans confirm there is definitely a new lesion, then progression should be declared using the date of the initial scan.
 - A lesion identified on a follow-up study in an anatomical location that was not scanned at baseline is considered a new lesion and will indicate disease progression, regardless of any response that may be seen in target or non-target lesions present from baseline.
- Subjects with a global deterioration of health status requiring discontinuation of treatment without objective evidence of disease progression at that time should be classified as having “symptomatic deterioration.” Every effort should be made to document the objective progression with an additional imaging assessment even after discontinuation of treatment.
- In some circumstances it may be difficult to distinguish residual disease from scar or normal tissue. When the evaluation of complete response (CR) depends on this determination, it is recommended that the residual lesion be further investigated by fluorodeoxyglucose-positron emission tomography (**FDG-PET**) or PET/computed tomography (**PET/CT**), or possibly fine needle aspirate/biopsy, to confirm the **CR** status.

Confirmation Measurement / Duration of Response

- **Response Confirmation** - In non-randomized trials where response is the primary endpoint, confirmation of PR and CR is required to ensure responses identified are not the result of measurement error.
- **Duration of overall response** – The duration of overall response is measured from the time measurement criteria are first met for CR/PR (whichever is first recorded) until the first date the recurrent or progressive disease is objectively documented.
- **Duration of Stable Disease** - SD is measured from the start of the treatment until the criteria for disease progression are met, taking as reference the smallest measurements recorded since the treatment started.

Approved

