Whenever DLRT will review the data, and there are at least 5 evaluable subjects in the tumor type, the futility and efficacy thresholds for that tumor type will be calculated using

all the cumulative efficacy data in phase 1 Monotherapy RP2D ORR Analysis Set to provide the guidance. In the calculation of thresholds, a response is defined as either a confirmed or unconfirmed CR or PR as per RECIST 1.1.

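### The phase 1 Go/NoGo count keeps responses whose confirmation has already failed, which moves the guidance toward Go and, mainly, away from NoGo

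*Supplement*

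**What the plan says.** Protocol Amendment 3, section 10.4.1.2, has the Dose Level Review Team (DLRT) compare cumulative responses in each tumor type with cut-offs derived from a Beta(1,1) prior. For NSCLC the guidance is Go if P(ORR > 0.25) is at least 60% and NoGo if P(ORR ≤ 0.15) exceeds 75%. For CRC the corresponding rates are 0.10 and 0.05. The count is defined thus: "In the calculation of thresholds, a response is defined as either a confirmed or unconfirmed CR or PR as per RECIST 1.1". SAP Amendment 1, section 7.1.2, has the same definition: "a response is defined as either a confirmed or unconfirmed CR or PR as per RECIST 1.1". Neither separates a response awaiting its confirmatory scan from one that was not confirmed.

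The ORR endpoints are stricter. For the phase 1 secondary ORR (Protocol 10.1.1.1.1.2), and in the same terms for the phase 2 primary ORR (10.1.1.2.1), "Complete response and PR require confirmatory CT or MRI repeat assessment 4 weeks after the first detection of response". Protocol Appendix D gives the reason: "confirmation of PR and CR is required to ensure responses identified are not the result of measurement error". Its table assigns PR followed by SD a best overall response of SD. The phase 2 benchmarks sit on nearly the same scale as the Go rates: "The benchmark ORR to exclude is selected as 23% for NSCLC and 10% for CRC".

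**The concern.** The cut-offs are fixed numbers of responders, stated as if the count estimated the true ORR. A subject with a PR at week 6 and SD at the next scan is a non-responder under Appendix D. Read plainly, the threshold definition still counts that subject, at that review and at every later one, because the data are cumulative. Extra counted responders against fixed cut-offs can only make Go more likely and NoGo less likely.

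What is at stake is the recommendation to open phase 2 in a tumor type or to stop for lack of activity. The margin is thin in CRC, where Table 11 recommends Go on one response among 5 to 12 subjects.

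**Working it through.** **1. Reproduce the cut-offs.** With r responses in n subjects, the posterior is Beta(1 + r, 1 + n − r). For NSCLC at n = 25:
- P(ORR > 0.25) is 0.685 with r = 7 (Go) and 0.515 with r = 6 (not Go).
- P(ORR ≤ 0.15) is 0.770 with r = 2 (NoGo) and 0.561 with r = 3 (not NoGo).

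These match Table 10. Across n = 5 to 60 both look-up tables reproduce, apart from a rounding-level tie in CRC at n = 52 (posterior 0.750005), which touches no printed result.

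**2. Reproduce the operating characteristics.** Exact recursion of the binomial count over looks at 5, 10, …, 60 gives, at 60 subjects:

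| | True ORR | Go, recomputed (printed) | NoGo, recomputed (printed) |
|---|---|---|---|
| NSCLC | 0.10 | 13.2% (13%) | 75.6% (76%) |
| NSCLC | 0.30 | 90.9% (91%) | 3.6% (4%) |
| CRC | 0.05 | 48.7% (49%) | 27.7% (28%) |
| CRC | 0.15 | 96.5% (96%) | 0.8% (1%) |

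The tables are sound for whatever rate is counted.

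**3. One failed response at one review.** This needs no assumed rate. For CRC at n = 10:
- 0 responses: P(ORR > 0.10) = 0.9^11 = 0.31, not Go.
- 1 response: 0.9^11 + 11 × 0.1 × 0.9^10 = 0.314 + 0.384 = 0.70, Go.

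If that one PR has already failed confirmation, the written rule says Go and the corrected rule does not.

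**4. Written rule against corrected rule.** The documents give neither a confirmation proportion c nor an accrual rate, so both are assumed. First response is placed at week 6 (P1OAS needs 6 weeks of data, Protocol 10.1.2.3) and confirmation is read at week 12 (the confirmatory scan may wait for the next scheduled one, 7.5). The probability of a counted response is the confirmed ORR divided by c; at c = 0.8 that is 0.15/0.8 = 0.1875 for NSCLC and 0.05/0.8 = 0.0625 for CRC. If A subjects accrue per 6 weeks in the tumor type, then at a look on n subjects the first n − A have had their week-12 scan read. The corrected rule removes the failed responses among those n − A; the written rule removes none. Results are by simulation, with looks every 5 subjects to 60 and the range covering A = 5, 10 and 20:

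| Confirmed ORR | c | Go: written | Go: corrected | NoGo: written | NoGo: corrected |
|---|---|---|---|---|---|
| NSCLC 15% | 0.9 | 38% | 36–38% | 34% | 38–41% |
| NSCLC 15% | 0.8 | 48% | 42–47% | 24% | 30–37% |
| NSCLC 15% | 0.7 | 61% | 49–58% | 16% | 22–33% |
| CRC 5% | 0.9 | 54% | 53% | 23% | 25–26% |
| CRC 5% | 0.8 | 59% | 57–59% | 18% | 21–24% |
| CRC 5% | 0.7 | 66% | 63–66% | 13% | 17–21% |

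**5. Sparser looks.** With looks at 10, 20, 40 and 60, c = 0.8 and A = 5, Go falls from 36% to 26% in NSCLC and from 58% to 52% in CRC. At A = 10 or 20 the fall is 4 points or less. Fewer looks leave more confirmation scans read by each one, so the correction does more.

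**The case against.** *The wording may already exclude failures.* The definition ends with a reference to RECIST 1.1, and Appendix D turns PR then SD into SD. That pulls the other way but does not settle it. In Appendix D an unconfirmed PR exists only as a time-point response, and a week-6 PR remains one after a later SD. If the sponsor meant to exclude failures, the text should say so.

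*The effect is modest, above all on Go in CRC.* This stands. Most of the Go probability arises at the earliest looks: Table 13 shows 40 of the 49 points at ORR 0.05 by n = 10. Unconfirmed responses at those looks are mostly still pending and rightly counted. CRC leniency comes chiefly from the chosen cut-off, and the plan prints it openly.

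*The guidance as a whole need not lean toward Go.* This also stands. A subject whose first response comes at week 12 counts as a non-responder at a week-6 review. If 30% of responses first appeared at week 12 (assumed, c = 0.8), Go under the written rule for NSCLC at 15% would be 39%, 32% and 27% for A = 5, 10 and 20, against 31% on mature confirmed responses. A reader might infer a net bias toward Go; the documents support only that this one component has a certain direction. Two opposing errors of unknown size are still no reason to keep a known failure in the count.

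*Safeguards exist.* The thresholds are guidance, the DLRT sees all efficacy data, and the decision rests on the totality of data (10.4.1.2). Phase 2 has its own futility looks, with CRC enrollment paused at the first (10.4.1.3.2).

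**Conclusion.** The point holds as a defect in a stated decision rule, of limited consequence. Under the week-6 and week-12 timing, looks every 5 subjects and 80% confirmation, correcting it lowers Go by about 1 to 6 points in NSCLC at 15% and 0 to 2 in CRC at 5%. NoGo rises by about 6 to 13 points in NSCLC and 3 to 6 in CRC. Sparse looks with slow accrual raise the Go effect to about 10 and 6 points. The direction is certain; the size depends on confirmation, accrual and review timing, none of which the documents give.

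Three stronger readings are not supported:
- A reader might take the jump in NSCLC Go from 31% to 48% (or CRC from 49% to 59%) as the effect. Those gaps compare confirmed-only counting with counting every unconfirmed response. Pending responses should count, so most of the CRC Go gap would remain after the fix.
- A reader might conclude that Tables 10 to 13 are wrong. They reproduce.
- A reader might fear for the efficacy conclusion. The primary analysis uses phase 2 subjects only, with confirmed and independently reviewed responses (Protocol 10.1.1.2.1, 10.5.1).

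**What to change.** In Protocol 10.4.1.2 and SAP 7.1.2, replace the definition with:

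> In the calculation of thresholds, a response is a confirmed CR or PR, or an unconfirmed CR or PR for which no evaluable assessment at least 4 weeks after first response is yet available and no progression, death or end of disease assessment has occurred by the data cutoff. A CR or PR that was not confirmed at an evaluable assessment at least 4 weeks later, or that was followed by progression, death or end of disease assessment without confirmation, counts as a non-response.

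The 4-week condition matters because extra scans are allowed (Protocol 7.5). A scan at less than 4 weeks that still shows response cannot confirm it, and must not turn a continuing responder into a failure.

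Keep the cut-offs and Tables 10 to 13 unchanged. Show the DLRT the confirmed, pending and failed counts by tumor type.

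The cost is one sentence in each document and a status flag on data already collected, with no extra scans and no delay to reviews. The downside is that a tumor type may occasionally need more expansion subjects before a Go recommendation, or receive a NoGo recommendation sooner.
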